7. EFFICACY ANALYSES

All efficacy analysis will be based on the PP population. This study will utilize the definitions of tumor response as described in Response Evaluation Criteria in Solid Tumors (RECIST) version 1.1 (Appendix 2).

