### 6.3 Treatment Duration and End of Study Definition

#### 6.3.1 Treatment Duration

Patients should continue on treatment with BBT-176 until RECIST v1.1 defined progression, unacceptable toxicities, symptomatic progression or until the criteria for treatment discontinuation criteria ([Section 9](#)) are met.

A patient is considered to have completed the study when all phases of the study, including the last visit or the last scheduled procedure shown in the Schedule of Activities (SoA; [Section 3.3](#)), have been completed.

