#### 10.1.1 Tumor Assessment (RECIST v1.1)

Tumor assessment (RECIST version 1.1) will be performed at Screening and every 6 weeks from Cycle 1 Day 1 until progression of disease, EOT, or until the patient commences further anti-cancer treatment, whichever comes first.

- Imaging may be performed within 7 days before the scheduled visit.
- In the event of a delay or discontinuation of study drug, tumor assessment should continue to follow the original schedule.

The Investigator will choose the anatomical extent and the modality of imaging study, while brain MRI is mandatory at screening. The assessment by the Investigator/local radiologist will be the basis for eligibility, continuation, or discontinuation of the trial in an individual patient.

[REDACTED]

[REDACTED]

[REDACTED]

[REDACTED]

[REDACTED]

[REDACTED]

[REDACTED]

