7.1 Tumor Response

Tumor assessment (RECIST version 1.1) will be performed at Screening and every 6 weeks from Cycle 1 Day 1 until progression of disease, EOT, or until the patient commences further anti-cancer treatment, whichever comes first. All efficacy data will be summarized [REDACTED]

[REDACTED] Baseline as well as change from baseline and percentage change from baseline measurements of the sum of the longest diameters for the target lesions will be summarized at each scheduled evaluation using descriptive statistics including mean, standard deviation, median, minimum and maximum values.

[figure not shown]

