7.1.1 Overall Time Point Response

[figure not shown]
The investigator's assessment of a patient's target lesion response, non-target lesion response, and appearance of new lesions (collected from the eCRF) will be used to determine the overall tumor response at each time point as shown [REDACTED]

The possible overall tumor responses at a time point, from best to worst, are as follows.

- Complete Response (CR)
- Partial Response (PR)
- Stable Disease (SD)
- Progressive Disease (PD)

[figure not shown]
If no assessment is done or a response cannot be determined, it is designated as Not Evaluable (NE).

[figure not shown]

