7.1.3 Best Overall Response

A Best Response is determined for each sequential pair of post-treatment time points (and in some cases, triplets of sequential time points). Then, the Best Overall Response for a patient (when confirmation of CR and PR are required) is the best of these Best Responses.

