7.2 Objective Response Rate (ORR)

The ORR will be estimated by the number of patients with a best overall response of CR or PR divided by the total number of patients who are evaluable for efficacy. The best overall response is the best response recorded from the start of the treatment until progression of disease, EOT, or until the patient commences further anti-cancer treatment, whichever comes first.

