7.7 Methods of Efficacy Analysis

The extent of disease will be assessed using the sum of the longest diameter from the target lesions. Change from baseline and percent change from baseline measurements will be summarized at each scheduled evaluation using descriptive statistics.

The investigators' assessments of patients' target lesion response, non-target lesion response, and appearance of new lesions (collected from the eCRF) are used to determine the overall [tumor] response at each time point as shown in Section 7.1.1. The investigators' assessments will be shown in listings.

Next, as indicated in Section 7.1.2, the best [tumor] response for sequential pairs (or triplets) of time point responses (recorded from the start of study treatment until the end of treatment) are determined as shown in Table 14 and in the subsequent discussion. Finally, as indicated in Section 7.1.3, the Best Overall Response for a patient—when confirmation of CR and PR are required—is the best of these Best Responses. The number and percent of patients in each category of Best Overall Response (CR, PR, SD, and PD) will be summarized by cohort.

The ORR will be presented with frequencies and percentages with 80% confidence interval. The frequency and percentages of patients with a best overall response of CR, PR, with stable disease (SD), or with PD will be summarized by cohort, additionally. 80% confidence intervals will be provided.

DoR will be summarized using the Kaplan-Meier estimate including median estimate, first quartile, 3rd quartile.

Progression-free survival in days will be summarized using the Kaplan-Meier to estimate the median PFS. The quartiles, including the median time-to-event and its two-sided 95% CI will be presented for each endpoint. Summaries will be presented for each cohort and overall.

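### The SAP gives two unlinked names for the Part 2 ORR denominator and leaves NE out of the best-overall-response summary, so treated patients without a scan may drop out of the primary estimate

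*SAP*

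**What the plan says.** ORR by RECIST 1.1 is the Part 2 primary endpoint (Protocol 5.3.2.1; SAP 2.1.1, Table 2). On who is counted and how:

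- **Population.** SAP 7: "All efficacy analysis will be based on the PP population". Readable text expands PP only as Per Protocol.
- **ORR denominator.** SAP 7.2: responders "divided by the total number of patients who are evaluable for efficacy". Response counts only up to progression, end of treatment (EOT) or further anti-cancer therapy, whichever is first.
- **Confirmation.** SAP 7.1.3: "the Best Overall Response for a patient (when confirmation of CR and PR are required) is the best of these Best Responses".
- **Missing assessments.** SAP 7.1.1 labels a time point NE when it has no assessment or no determinable response. SAP 7.5 says missing values are not imputed.
- **Summary.** SAP 7.7: "The number and percent of patients in each category of Best Overall Response (CR, PR, SD, and PD) will be summarized by cohort". NE is not among the categories. ORR gets an 80% confidence interval.
- **Scans.** SAP 7.1: at Screening, then "every 6 weeks from Cycle 1 Day 1 until progression of disease, EOT, or until the patient commences further anti-cancer treatment, whichever comes first". Protocol 10.1.1 adds: "Imaging may be performed within 7 days before the scheduled visit".
- **Stopping.** Protocol 6.3.1: treatment continues "until RECIST v1.1 defined progression, unacceptable toxicities, symptomatic progression", or until the discontinuation criteria are met.

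The definitions of the analysis populations (SAP 5, Protocol 11.2) are not readable. Protocol 11.6.1 is mostly redacted; a surviving fragment refers to an evaluable population that is reported additionally.

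**The concern.** The primary estimate of a single-arm phase depends on which treated patients enter its denominator. The SAP names that set in two ways and does not connect them in readable text. It also creates an NE status that has no place in the summary from which ORR is read.

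The patients affected are those who stop early. Toxicity or symptomatic progression can end treatment before any on-treatment scan. If membership of the PP or evaluable set depends on having a post-baseline assessment, these patients disappear from the denominator, although each was treated and none can have responded under the SAP's rules. Without an NE category, the four listed categories need not add up to the number treated, and the best-response summary would not show the shortfall.

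No control arm offsets this. The reported ORR and its interval are the main efficacy result of Part 2.

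**Working it through.** The plan gives no figure to reproduce: the Part 2 sample size is redacted and Part 2 has no efficacy hypothesis (Protocol 3.1, Statistical Methods).

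**1. When the first scan falls.** Six weeks from Cycle 1 Day 1 is Day 1 + 42 = Day 43. With the 7-day window the earliest is Day 43 - 7 = Day 36.

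**2. Why an unscanned patient can only be a non-responder.** SAP 7.2 counts no response after EOT, and SAP 7.1.3 derives best overall response from sequential post-treatment time points. A patient with no scan before EOT has no response to count.

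**3. Effect of leaving such patients out.** Let N be the number treated, x the responders and d the share of treated patients left out, all non-responders.

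ORR (all treated) = x/N. ORR (evaluable) = x/[N(1-d)] = (x/N) × 1/(1-d).

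The factor is 1/0.95 = 1.05 at d = 5%, 1/0.90 = 1.11 at 10% and 1/0.80 = 1.25 at 20%. The documents give no value for d, and it may be zero.

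**4. Illustration.** Assumptions: N = 30 and N = 12 are borrowed from the Part 1 RP2D exploratory cohorts in Protocol 12.8 (maximum of 30 per cohort; review once twelve patients have data). Responder counts are assumed. The interval is the exact (Clopper-Pearson) 80% interval, since readable text fixes the level but not the method. Its limits are the 0.10 quantile of Beta(x, n-x+1) and the 0.90 quantile of Beta(x+1, n-x), with n the denominator.

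| Treated | Responders | Left out | ORR | 80% CI |
|---|---|---|---|---|
| 30 | 9 | 0 | 9/30 = 30.0% | 19.0 to 43.2 |
| 30 | 9 | 1 | 9/29 = 31.0% | 19.7 to 44.5 |
| 30 | 9 | 3 | 9/27 = 33.3% | 21.2 to 47.5 |
| 30 | 9 | 6 | 9/24 = 37.5% | 24.1 to 52.6 |
| 30 | 6 | 0 | 6/30 = 20.0% | 10.9 to 32.5 |
| 30 | 6 | 3 | 6/27 = 22.2% | 12.1 to 35.8 |
| 30 | 6 | 6 | 6/24 = 25.0% | 13.7 to 39.8 |
| 12 | 3 | 0 | 3/12 = 25.0% | 9.6 to 47.5 |
| 12 | 3 | 1 | 3/11 = 27.3% | 10.5 to 51.1 |
| 12 | 3 | 2 | 3/10 = 30.0% | 11.6 to 55.2 |

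**5. Exclusions for other reasons.** If the PP set drops k responders and m non-responders for protocol violations, ORR becomes (x-k)/(N-k-m). This is below x/N whenever k/(k+m) exceeds x/N. For example, dropping one responder from 9/30 gives 8/29 = 27.6%. The upward direction in step 3 therefore holds for unscanned patients only.

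**The case against.** The strongest reply is that the missing link between the two terms may be a product of redaction. Population definitions belong in SAP 5 and Protocol 11.2, and neither can be read. A rule for missing assessments may stand in SAP 7.1.2 (table and bullets redacted), in Protocol 11.6.1 or in another blacked-out part. This stands: the plan cannot be faulted for lacking definitions, and exclusion of early stoppers can be neither confirmed nor ruled out.

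Some readable text also points the other way:

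- SAP 7.4 has a PFS rule for patients who stop for clinical progression without an assessment. PFS falls under the PP statement, which suggests, without proving, that PP keeps such patients.
- SAP 4.2.2 takes percentages relative to the total number of subjects. If that governs the best-response summary, any remainder would be visible. SAP 7.2 is more specific for ORR, however.
- Protocol 10.1.1 says scans keep their original schedule after study drug is discontinued, and Protocol 9.2 sends discontinued patients to EOT procedures in a schedule that is not readable. Either could leave fewer patients unscanned, though Protocol 10.1.1 also ends assessment at EOT.
- The fragment in Protocol 11.6.1 suggests that the evaluable set may be reported beside another set. The SAP is dated 28 January 2021, while the Protocol cites a May 2021 publication, so SAP 7 may lag behind the Protocol. If so, its statement that all efficacy analysis uses PP needs reconciling.
- SAP 6.1 reports the number in each analysis population, so exclusions would be countable.

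These points reduce the likely size. None supplies a readable rule for a patient who remains unassessed, and none puts NE in the list in SAP 7.7.

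A reader might infer that the plan does inflate ORR, or that the reported ORR must exceed the all-treated one. The documents support neither: no readable sentence ties PP membership to having a scan, and exclusions for violations can lower ORR. Nor can one say that the finished table has no NE row. No table shell is visible; only the category list in the text omits NE.

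**Conclusion.** The point holds in conditional form. Readable, unredacted sentences name the ORR set in two ways without joining them, and list best-overall-response categories without the NE status that the SAP itself creates. If either set requires a post-baseline assessment, the Part 2 ORR rises by 1/(1-d) for treated patients without a scan. In the illustration, 3 of 30 left out moves 30.0% to 33.3%, well inside the original 80% interval of 19.0 to 43.2.

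This rests on an assumed cohort size, assumed responder counts, an assumed exact interval and a share d that may be zero. Part 2 tests no hypothesis, so the effect is on a descriptive estimate and its interval, with no consequence for type I error or power. Severity is minor to moderate. The change is worth making because it is cheap and makes the primary denominator explicit.

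**What to change.** In SAP 7, 7.2 and 7.7:

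1. Report the Part 2 ORR with all patients who received at least one dose of BBT-176 as the denominator, and write that definition out. Count NE, or no post-baseline assessment, as non-response.
2. Add an NE category to the best-overall-response summary so that its rows sum to that denominator.
3. Keep the PP or evaluable-set ORR as a supportive analysis.
4. Use one named term for the evaluable set in SAP 7, SAP 7.2 and Protocol 11.6.1.

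If a redacted section already counts unassessed patients as non-responders, only items 2 and 4 are needed. No change to the PFS or DoR set is asked for.

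The cost is SAP wording and one extra table. The downside is a possibly slightly lower stated ORR.

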7.1 Tumor Response

Tumor assessment (RECIST version 1.1) will be performed at Screening and every 6 weeks from Cycle 1 Day 1 until progression of disease, EOT, or until the patient commences further anti-cancer treatment, whichever comes first. All efficacy data will be summarized [REDACTED]

[REDACTED] Baseline as well as change from baseline and percentage change from baseline measurements of the sum of the longest diameters for the target lesions will be summarized at each scheduled evaluation using descriptive statistics including mean, standard deviation, median, minimum and maximum values.

[figure not shown]
7.1.1 Overall Time Point Response

[figure not shown]
The investigator's assessment of a patient's target lesion response, non-target lesion response, and appearance of new lesions (collected from the eCRF) will be used to determine the overall tumor response at each time point as shown [REDACTED]

The possible overall tumor responses at a time point, from best to worst, are as follows.

- Complete Response (CR)
- Partial Response (PR)
- Stable Disease (SD)
- Progressive Disease (PD)

[figure not shown]
If no assessment is done or a response cannot be determined, it is designated as Not Evaluable (NE).

[figure not shown]

7.1.2 Best Response

The best responses for pairs of time point responses (when confirmation of CR and PR are required) are determined as shown

STATISTICAL ANALYSIS PLAN
BBT176-ONC-001

- [REDACTED]
- [REDACTED]
- [REDACTED]

7.1.3 Best Overall Response

A Best Response is determined for each sequential pair of post-treatment time points (and in some cases, triplets of sequential time points). Then, the Best Overall Response for a patient (when confirmation of CR and PR are required) is the best of these Best Responses.

7.2 Objective Response Rate (ORR)

The ORR will be estimated by the number of patients with a best overall response of CR or PR divided by the total number of patients who are evaluable for efficacy. The best overall response is the best response recorded from the start of the treatment until progression of disease, EOT, or until the patient commences further anti-cancer treatment, whichever comes first.

7.3 Duration of Response (DoR)

DoR is calculated for every patient with a response to therapy (PR and CR) and is defined as the number of days from the date of initial response to the date of the first documented disease progression/relapse (including clinical progression) or death, whichever occurs first. The exact date of a response is based on the tumor response assessment dates as defined in Section 7.1.1. If disease progression/relapse does not occur, DoR is censored as of the date of their last imaging exam of target or non-target lesions. Patients without an assessment of disease progression/relapse who discontinue the study and indicate progressive disease or clinical progression as the primary reason for ending treatment will be counted as having progressed on their last dose date of BBT-176—whichever date is earlier.

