7.4 Progression-Free Survival (PFS)

PFS will be calculated for each patient as the number of days from the first day of treatment to the date of the first documented disease progression/relapse or date of death, whichever occurs first. The exact date of disease progression is based on the tumor response assessment dates as indicated in Section 7.1.1. If disease progression/relapse does not occur, PFS is censored as of the date of their last imaging exam of target or non-target lesions. However, for patients without an assessment of disease progression/relapse who escalate to a higher dose, PFS is censored as of the date of their first dose of study medication in the later dose cohort. Patients without an assessment of disease progression/relapse who discontinue the study and indicate progressive disease or clinical progression as the primary reason for ending treatment will be counted as having progressed on their last dose date of BBT-176—whichever date is earlier.

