In non-randomized trials where response is the primary endpoint, confirmation of PR and CR is required to ensure that the identified responses are not the result of measurement error. This will also permit appropriate interpretation of results in the context of historical data where response has traditionally required confirmation in such trials. However, in all other circumstances, i.e., in randomized trials (phase 2 or 3) or trials where stable disease or progression are the primary endpoints, confirmation of response is not required since it will not add value to the interpretation of trial results. However, elimination of the requirement for response confirmation may increase the importance of central review to protect against bias, in particular in trials which are not blinded.

In the case of SD, measurements must have met the SD criteria at least once after trial entry at a minimum interval (in general not less than 6 to 8 weeks) that is defined in the trial protocol.

Duration of Overall Response

The duration of overall response is measured from the time that measurement criteria are first met for CR/PR (whichever is first recorded) until the first date that recurrent or progressive disease is objectively documented (taking as reference for progressive disease the smallest measurements recorded on study).

The duration of overall complete response is measured from the time measurement criteria that are first met for CR until the first date that recurrent disease is objectively documented.

Duration of Stable Disease

Stable disease is measured from the start of the treatment (in randomized trials, from date of randomization) until the criteria for progression are met, taking as reference the smallest sum on study (if the baseline sum is the smallest, this is the reference for calculation of PD).

The clinical relevance of the duration of stable disease varies in different studies and diseases. If the proportion of patients achieving stable disease for a minimum period of time is an endpoint of importance in a particular trial, the protocol should specify the minimal time interval required between two measurements for determination of stable disease.

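### SAP 7.3 and 7.4 handle clinical progression differently, so DoR and PFS can disagree for the same responder when the last-dose-date rule they share does not apply

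*SAP*

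**What the plan says.** DoR and PFS are secondary endpoints in Part 2 and exploratory in Part 1, in each case per RECIST 1.1 (Protocol 5.3; SAP Tables 4 and 5).

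- **DoR, SAP 7.3.** The response ends at "the date of the first documented disease progression/relapse (including clinical progression) or death, whichever occurs first". The section ties the date of a response to the tumor assessments but gives no separate date for clinical progression.
- **PFS, SAP 7.4.** Time runs from "the first day of treatment to the date of the first documented disease progression/relapse or date of death, whichever occurs first". The next sentence adds a dating rule: "The exact date of disease progression is based on the tumor response assessment dates as indicated in Section 7.1.1".
- **Fallback, identical in both sections.** It covers "Patients without an assessment of disease progression/relapse who discontinue the study" and who give "progressive disease or clinical progression as the primary reason for ending treatment will be counted as having progressed on their last dose date". A closing phrase then takes the earlier date, although only one date has been named.
- **Dose escalation, SAP 7.4 only.** For patients without an assessed progression who move to a higher dose, "PFS is censored as of the date of their first dose of study medication in the later dose cohort". SAP 7.3 has no such rule.
- **RECIST text, SAP Appendix 2.** Duration of response runs "until the first date that recurrent or progressive disease is objectively documented". The appendix treats symptomatic deterioration as a reason for stopping therapy, not as a category of objective response.

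**The concern.** For a responder, DoR and PFS should normally end on the same day and with the same status, because they differ only in where the clock starts. Here the main DoR definition admits an event that the main PFS definition does not. One patient could then be an event in the DoR Kaplan-Meier analysis and censored, or an event on a later date, in the PFS analysis.

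DoR is estimated among responders only, so a few such patients may matter to its median and quartiles. The trial is open-label and response is assessed by the investigator. If the wording is left open, event dates may be settled at programming, with the data in view. A DoR that can end on clinical grounds is also not the RECIST endpoint that the protocol names.

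**Working it through.** The plan gives no figure on this point to reproduce. The check sets the rules side by side and applies them to one illustrative responder.

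**When the fallback applies.** Three conditions must hold together: no assessment of progression, study discontinued, and progressive disease or clinical progression as the primary reason for ending treatment. If any one fails, only the main definitions remain, and those differ.

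**Inputs from the documents.** Scans fall every 6 weeks from Cycle 1 Day 1 (SAP 7.1), so nominally on Days 43, 85 and 127. Durations are the later date minus the earlier date plus 1 (SAP 4.2.3). Without progression, both endpoints are censored at the last imaging exam.

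**Assumed for illustration.** Partial response on Day 43, confirmed on Day 85; clinical progression on Day 100. In A to C the last dose is also on Day 100.

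| Pattern | DoR, read with the parenthesis as a separate event | PFS | Consistent? |
|---|---|---|---|
| A. Leaves the study with clinical progression as primary reason; no scan shows progression | Event Day 100: 100 − 43 + 1 = 58 days | Event Day 100: 100 − 1 + 1 = 100 days | Yes |
| B. As A, but a Day 127 scan shows progression | Event Day 100: 58 days | Event Day 127: 127 − 1 + 1 = 127 days | No: 127 − 100 = 27 days apart |
| C. Clinical progression recorded, but another primary reason for ending treatment; last scan Day 85 | Event Day 100: 58 days | Censored Day 85: 85 − 1 + 1 = 85 days | No: event against censoring |
| D. Stays on treatment and study; Day 127 scan shows no progression | Event Day 100: 58 days | Still running | No: event against no event |

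Time from first dose to response is 43 − 1 = 42 days. In A, 42 + 58 = 100, which equals PFS. In B, 42 + 58 = 100 against a PFS of 127. If DoR were dated from the scan in B, it would be 127 − 43 + 1 = 85 days, and 42 + 85 = 127.

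**Size of the gap in pattern B.** If the next scheduled scan shows progression, the gap is at most about one interval: 6 × 7 = 42 days on the nominal schedule. The documents give no expected DoR. If it is assumed to be 4 to 6 months:

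- 42 / (4 × 30.4375) = 42 / 121.75 = 0.34
- 42 / (6 × 30.4375) = 42 / 182.625 = 0.23

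These are ceilings for one affected responder on an assumed duration. They do not estimate the shift in a median.

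**Can B to D arise?** Protocol 6.3.1 lists symptomatic progression among the reasons for ending treatment. Protocol 10.1.1 keeps scans on the original schedule after study drug is discontinued, yet also names end of treatment as a point where assessment stops. SAP Appendix 2 urges that objective progression be documented even after treatment ends. Scans after clinical progression are therefore contemplated, but how often they would occur cannot be derived.

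**Dose escalation.** A responder who escalates without assessed progression has PFS censored at the first dose in the later cohort while DoR keeps running. This is a second mismatch, independent of clinical progression. The protocol describes intra-patient escalation under Part 1.

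**The case against.** A reader might infer that PFS ignores clinical progression altogether. The documents do not support that. The last sentence of SAP 7.4 makes it a PFS event on the last dose date, exactly as SAP 7.3 does for DoR. Since symptomatic progression is a listed reason for ending treatment and one of the scanning rules stops at end of treatment, pattern A may well be the usual path, and there the endpoints agree. This objection stands and limits the point to the patterns outside the fallback.

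A second objection is that SAP 7.3 never gives a clinical date. The only date it attaches to clinical progression is the last dose date, so the parenthesis may merely anticipate the closing sentence. On that reading the two definitions match and the gap in pattern B disappears. The reading is possible, and so the point says that DoR *can* end at the clinical date. It does not settle the matter: the parenthesis sits in the main definition, and SAP 7.4 carries the same closing sentence without it.

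A third objection is that it would be one-sided to fault DoR alone against RECIST. That is correct, because the shared fallback takes PFS away from objectively documented progression as well.

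Finally, Protocol 11.6.2 and 11.6.3, SAP 7.6 and part of SAP 7.1.1 are blacked out and might settle event or date rules. Part 2 states no efficacy hypothesis and is summarised descriptively, which limits the consequences.

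**Conclusion.** The point holds in limited form. The visible definitions differ on clinical progression and, outside the shared fallback, can give one responder inconsistent DoR and PFS outcomes. For an affected responder this means either different event dates, up to about 6 weeks apart if the next scheduled scan shows progression, or an event in DoR with no matching PFS event. The 23% to 34% figures are upper bounds that rest on an assumed DoR of 4 to 6 months.

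The documents do not support a general statement that DoR is biased short. That would need the frequency of patterns B to D, which is unknown. Nor do they support confining the departure from RECIST to DoR. The Part 2 primary endpoint, objective response rate, is not affected. What remains is an inconsistency between two secondary endpoints that is cheap to remove before the data are analysed.

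**What to change.** 1. Delete the parenthesis on clinical progression from the main definition in SAP 7.3, and apply the tumor-assessment dating rule of SAP 7.4 to DoR.
2. Use one event and censoring definition for both endpoints: RECIST-documented progression or death. Deleting the parenthesis alone is not enough, because the fallback would remain in both sections.
3. Treat the fallback in one of two ways. Either move it to a single labelled sensitivity analysis applied identically to DoR and PFS, or keep it as one common rule with a single stated event date. In both cases resolve the closing phrase that takes the earlier of two dates when only one is named.
4. Apply the censoring rule for intra-patient dose escalation to both endpoints or to neither.
5. Reconcile the two statements in Protocol 10.1.1 on scanning after discontinuation, so that it is clear which later scans can count.

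The cost is a small SAP edit, a protocol clarification and an optional extra table. If the fallback moves to a sensitivity analysis, some patients with clinical progression and no scan become censored in the main analysis. The sensitivity analysis would show how much that matters.

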Progressive Disease (PD): At least a 20% increase in the sum of diameters of target lesions, taking as reference the smallest sum on study (this includes the baseline sum if that is the smallest on study). In addition to the relative increase of 20%, the sum must also demonstrate an absolute increase of at least 5 mm. (Note: the appearance of one or more new lesions is also considered progression).

Stable Disease (SD): Neither sufficient shrinkage to qualify for PR nor sufficient increase to qualify for PD, taking as reference the smallest sum diameters while on study.

Lymph nodes. Lymph nodes identified as target lesions should always have the actual short axis measurement recorded (measured in the same anatomical plane as the baseline examination), even if the nodes regress to below 10 mm on study. This means that when lymph nodes are included as target lesions, the “sum” of lesions may not be zero even if complete response criteria are met, since a normal lymph node is defined as having a short axis of < 10 mm. Case report recorded in a separate section where, in order to qualify for CR, each node must achieve a short axis < 10 mm. For PR, SD and PD, the actual short axis measurement of the nodes is to be included in the sum of target lesions.

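### DoR and PFS are censored at the last imaging exam whether or not it was evaluable, which can only leave the Kaplan-Meier estimates unchanged or raise them

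*SAP*

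**What the plan says.** SAP 7.3, for a responder without progression or relapse: "DoR is censored as of the date of their last imaging exam of target or non-target lesions". SAP 7.4 repeats the rule: "PFS is censored as of the date of their last imaging exam of target or non-target lesions". Both sections tie the dates of response or progression to the assessments of SAP 7.1.1, but the censoring date has no such tie.

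SAP 7.1.1 has a category for uninformative assessments: "If no assessment is done or a response cannot be determined, it is designated as Not Evaluable (NE". The response table in SAP Appendix 2 gives NE when target lesions are not all evaluated, non-target disease is not progressing and no new lesion is seen. Protocol 10.1.1 makes incomplete exams possible: "The Investigator will choose the anatomical extent and the modality of imaging study".

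Two rules take some patients out of the censoring rule. Those who stop for progressive disease or clinical progression without an assessment "will be counted as having progressed on their last dose date of BBT-176" (SAP 7.4; SAP 7.3 has the same rule). For patients who escalate dose without progression, "PFS is censored as of the date of their first dose of study medication in the later dose cohort".

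SAP 7.5 says only that missing values are not imputed. SAP 7.6, parts of SAP 7.1.1 and 7.1.2, and most of Protocol 11.6.2 and 11.6.3 are blacked out.

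**The concern.** A censoring date should be the last date on which the patient was known to be free of progression. Because the rule accepts an exam of target or non-target lesions, imaging of some lesions is enough to move the date. The SAP can thus call an exam NE and still count the patient as progression-free up to it. Patients who stop for toxicity, withdraw or are lost after such an exam are exposed to this.

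DoR and PFS are secondary endpoints in Part 2 and exploratory in Part 1. The trial has one arm, so no concurrent control would share an upward shift, and readers will judge the medians on their face.

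**Working it through.** The plan states no median PFS or DoR, event count or NE rate, so there is no figure to reproduce. The check has four steps.

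**1. Direction (PFS and DoR).** The Kaplan-Meier estimate is S(t) = product over event times of (1 − d/n), with d events among n at risk. Moving one patient's censoring date later adds 1 to n at each event time in between and leaves every d unchanged. Each factor 1 − d/n stays the same or rises, so S(t) and the median do too.

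**2. Size (PFS only, simulated).** From the documents: scans every 6 weeks, up to 7 days early (Protocol 10.1.1). Assumed: exponential progression with median 12, 18 or 26 weeks; cut-off at 54 weeks; each scan NE with probability 5%, 10% or 20%; progression never seen on an NE scan; 5% or 10% of patients leaving after each scan without progression. In a second set, 10% leave after an evaluable scan and 50% after an NE scan. Each scenario has 20,000 patients. A selection, with the SAP rule first and last-evaluable censoring second:

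| NE per scan; leaving | True median (wk) | Patients whose date moves | 24-week PFS | Difference (points) | Estimated median (wk) |
|---|---|---|---|---|---|
| 10%; unrelated, 10% | 12 | 3.3% | 25.1% / 24.7% | 0.4 | 17.1 / 17.1 |
| | 18 | 4.0% | 38.5% / 38.1% | 0.4 | 18.0 / 18.0 |
| | 26 | 5.0% | 52.6% / 52.3% | 0.3 | 29.4 / 29.3 |
| 10%; 50% after NE | 12 | 13.2% | 25.9% / 24.0% | 1.9 | 17.1 / 12.0 |
| | 18 | 16.1% | 39.8% / 37.7% | 2.1 | 23.1 / 17.9 |
| | 26 | 18.1% | 52.8% / 51.0% | 1.8 | 29.4 / 29.1 |
| 20%; 50% after NE | 12 | 25.2% | 27.4% / 23.2% | 4.2 | 17.3 / 17.0 |
| | 18 | 28.9% | 41.2% / 36.9% | 4.3 | 23.3 / 17.9 |
| | 26 | 33.5% | 54.9% / 51.0% | 3.9 | 29.7 / 29.1 |

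Across all unrelated scenarios, 0.9% to 10.4% of patients change date, 24-week PFS differs by 0.0 to 0.9 points and the median by at most about 0.1 week. Across all tied scenarios, 6.6% to 33.5% change date, 24-week PFS differs by 0.9 to 4.3 points and the median by 0.1 to 5.4 weeks. The median moves in jumps because events fall only on scan dates.

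**3. Small cohorts.** With 30 patients (the ceiling for an RP2D exploratory cohort, Protocol 12.8), true median 18 weeks and 1,500 simulated trials per setting, the median was identical under both rules in 98%, 91% and 83% of trials in three unrelated settings. It was identical in 66% and 41% in two tied settings. The SAP rule never gave the lower median.

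**4. Difference between rules versus error.** The differences above are not errors against the truth. Take a 122-day median, scan dates spread over the 7-day window, and 10% of those at risk ending on an NE exam at every scan. PFS at 168 days is then 41.5% under the SAP rule and 37.5% under last-evaluable censoring, against 39.2% true: 41.5 − 39.2 = 2.3 points high and 39.2 − 37.5 = 1.7 low. In the tied 18-week scenario with 10% NE, the model value at 24 weeks is 2^(−24/18) = 39.7%, against 39.8% and 37.7%. The low reading has a separate cause: a patient censored early in a scan window leaves the risk set before later-dated events of the same scan round.

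**The case against.** - **A partial exam is not blind.** SAP Appendix 2 says that "the appearance of one or more new lesions is also considered progression", and unequivocal non-target progression also counts, whatever the target lesions show. An exam rated NE because targets were missed has excluded those two routes. This stands: only target-lesion progression goes unassessed, and the simulated shifts are upper bounds for the NE rates assumed.
- **Other rules narrow the group.** Unassessed progression given as the reason for stopping is an event, and dose escalators have their own PFS rule. This stands, but patients leaving for other reasons remain.
- **A rule may sit in the redacted text.** That cannot be excluded. The point concerns the readable text, where the censoring sentence is explicit and unqualified.
- **Nothing formal depends on these medians.** The Protocol synopsis assumes no efficacy hypothesis, and no readable decision rule uses them. This limits the importance of the point.

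A reader might infer that both medians are inflated in every case. The documents do not support that. Only non-progressing patients whose last exam is NE are affected, no NE rate is given, and DoR was covered by the algebra alone. Nor do they support assuming that 10% of patients at risk end on an NE exam at every scan, which would mean about 33% of all patients finishing on one.

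**Conclusion.** The point holds as a conditional one, and the change is a cheap improvement. As readable, SAP 7.3 and 7.4 let an NE exam move the censoring date, and relative to last-evaluable censoring any effect on the curve or median is upward. For PFS the effect is under about 1 point at 24 weeks if NE exams are unrelated to leaving. It is roughly 1 to 4 points, with up to about one scan interval on the median, if NE exams are closely tied to leaving. These sizes rest on the assumed NE and drop-out rates, exponential progression and no detection on NE scans.

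A reader might also infer that the change would make the estimates unbiased, or always nearer the truth. Step 4 shows otherwise once scan dates vary within the window. The reason to change is that the censoring date should be one at which progression status was assessed; an upward error that happens to offset a downward one is no reason to keep the rule.

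**What to change.** In SAP 7.3 and 7.4, replace the last-imaging date with the date of the last tumor assessment whose overall time-point response under SAP 7.1.1 is CR, PR or SD. State that NE assessments, and imaging not recorded as a RECIST time point, do not move the date. For PFS, add that a patient with no evaluable post-baseline assessment and no event is censored at the first day of treatment. DoR needs no such addition, since a responder has at least the assessment that showed the response. The rules for dose escalation and for unassessed progression can stay as they are.

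A useful extra is to report how many patients had an NE last exam, with the last-imaging date as a sensitivity analysis.

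The cost is a small edit in two sections and one derivation, with no new data. Reported PFS and DoR may be slightly shorter.
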